7.4.5 Statistical/Analytical Issues

7.4.5.1 Handling of Dropouts or Missing Data

Data imputation on missing or indeterminate SoR from the Central Truth Panel on the reference lesion (i.e. subject level only) will be performed according to the following chart:

If the SoR determined by the CTP is not positive/negative then the SoR will be determined using the following rules:

1. If the subject has neurological deterioration at any time during the 6-months follow-up, the SoR will be assigned to positive.
2. If the subject is confirmed not to have neurological deterioration on or after day 141 (6 months with a 4-week time window, i.e. day 169 with a 28-day time window), even if the subject dies after day 141, the SoR will be assigned to negative.
3. Otherwise the SoR will remain as indeterminate.

All subject-level analysis involving SoR will be presented twice, by imputing the remaining indeterminate results as follows:

1. Main analysis of primary and secondary endpoints on subject level diagnostic performance – for each PET reader, the worst case according to that reader (i.e. the opposite finding to the individual PET reader finding) will be imputed
2. Sensitivity analysis 1 of primary and secondary endpoints on subject level diagnostic performance - for each PET reader, the worst case according to the majority of PET readers (i.e. the opposite finding to the PET finding of at least 2/3 PET readers)

To check the validity of the results based on the site's determination of the reference equivocal lesions, these lesions will be measured and confirmed by the central neuroradiologist. A sensitivity analysis on the main endpoint of subject level PPA and NPA, using only subjects with central neuroradiologist confirmation of the reference equivocal lesions, will be performed if there is discrepancy between the site confirmation of reference equivocal lesions vs the central neuroradiologist confirmation.

For lesion level analysis, none of the lesions will be imputed if the SoR designation from the CTP is missing or indeterminate. Lesion-level analysis will only include lesions with SoR designation of positive or negative by the CTP.

7.4.5.2 *Interim Analyses and Data Monitoring*

Not applicable.

7.4.5.3 *Multicenter Studies*

This is a multicenter study, with approximately 18 sites expected to participate. Data collected from all study sites will be pooled for data analysis.

7.4.5.4 *Multiple Comparisons/Multiplicity*

There will be no adjustments for multiple comparisons in the efficacy analysis for this study.

7.4.5.5 *Examination of Subgroups*

Subgroup analysis will be performed as described in section 7.4.4.3.

7.5 **Safety Evaluation**

Safety analysis will be carried out for the Safety analysis set, to include all subjects who have been dosed with IMP. Subjects who do not complete the study, for whatever reason, will have all available data up until the time of termination included in the analysis.

7.5.1 *Extent of Exposure*

Each subject will receive a single dose of ¹⁸F-fluciclovine by injection, 185 MBq (5 mCi) \pm 20%, delivered as an intravenous bolus by site staff. IMP administration data will be summarized, and details of administration will also be listed.

7.5.2 *Adverse Events*

Treatment-emergent adverse events are defined as those AEs with onset after the dose of IMP, or existing events that worsened after the dose of IMP during the study, up to 1 day following IMP administration. Events reported with a partial onset date (e.g., month and year are reported but the day is missing) will be considered to be treatment-emergent if it

cannot be confirmed that the event onset was prior to the dose of IMP based on the available date entries.

Adverse event verbatim terms will be coded to preferred terms and system organ classes using the latest version of MedDRA, version 23.0. Severity of AEs will be graded using the National Cancer Institute common terminology criteria for adverse events (NCI-CTCAE) v5.0.

Summaries that are displayed by system organ class (SOC) and preferred term (PT) will be ordered by descending incidence of SOC and PT within each SOC, and then alphabetically for SOC, and PT within SOC. Summaries of the following types will be presented:

- Overall summary of subject incidence of TEAEs by severity, relationship, and action taken, subject incidence of treatment-emergent serious adverse events (TESAEs) by relationship;
- Subject incidence of TEAEs by MedDRA system organ class and preferred term;
- Subject incidence of TEAEs by NCI-CTCAE grade, MedDRA system organ class, and preferred term;
- Subject incidence of TEAEs related to IMP by MedDRA system organ class, and preferred term;
- Subject incidence of TESAEs by MedDRA system organ class and preferred term;
- Subject incidence of TESAEs related to IMP by MedDRA system organ class and preferred term;

At each level of summarization (e.g., any AE, SOC, and PT), subjects experiencing more than one TEAE will be counted only once. For each subject and each adverse event, the worst severity recorded will be attributed and used in the by-severity summaries.

A by-subject listing of all adverse events (including non-treatment-emergent events) will be provided. This listing will include: subject identifier, age, sex, race, adverse event (SOC, PT, and verbatim term), date of onset and study day of onset, date of resolution and study day of resolution, duration, severity, seriousness, action taken, outcome and causality.

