9.1.8. Clinical Follow-Up / Data Abstraction

Clinical follow-up will be performed as SoC per local practice and is anticipated to vary between subjects. For study purposes, clinical data accrued during the period of clinical follow-up, pertaining to the ongoing assessment, eventual confirmation of diagnosis, and treatment of the lesions, will be collected. The data will comprise of brain imaging scans, treatment regimens, histopathological reports and mortality status, see [Table 1](#). Treatment regimens will pertain to treatments and therapies for the brain lesion(s) and primary tumor. These will include and are not limited to systemic treatments such as chemotherapy, immunotherapy and corticosteroids; and localized therapies such as radiotherapy, LITT and

craniotomy, see [Section 9.1.1](#). The period of data accrual will be up to 6 months following ¹⁸F-fluciclovine PET, or death, whichever comes first.

At this visit, an assessment will be performed to evaluate if the patient had experienced neurological deterioration potentially related to progression of brain metastases over the study period. This assessment will be performed by a site investigator who is a board-certified neuro-oncologist, radiation oncologist, medical oncologist or neurosurgeon. As with the other items at this Visit, this assessment will be based on an investigator review of the subject medical record and will take place in the physical absence of the subject.

Based on a review of the subject medical record at the Month 6 Follow-Up visit, the investigator will ascertain if the patient had demonstrated neurological deterioration over the 6-month period. This must be evidenced by one of the following as assessed by the investigator:

1. Notable clinical deterioration corresponding to a significant decline in Karnofsky Performance Status:
 - a. baseline 90/100 decreasing to \leq 70, or
 - b. baseline \leq 80 decrease by \geq 20, or
 - c. any baseline decreasing to \leq 50
2. New or persistent/worsening focal neurological deficit with neuro-anatomical correlation to the site of the reference lesion

If one of the criteria are met, the investigator must also confirm that this impairment:

- Lasted for at least 7 days, and
- Was not attributable to co-morbid events, treatment-related toxicity, changes in corticosteroid dose or progression of systemic disease, and
- Was not altered by therapies for radiation necrosis

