10.6. Visit 5 – Month 6 Follow-up (183 days ± 14 days)

All subjects will be followed for 6 months (183 days ± 14 days) following ¹⁸F-fluciclovine PET in order to collect diagnostic information (brain imaging scans, histopathological reports) and treatment regimens which will be provided to the Central Truth Panel ([Section 11.8](#)). Treatment regimens will pertain to treatments and therapies for the brain lesion(s) and primary tumor. These will include and are not limited to systemic treatments such as chemotherapy, immunotherapy and corticosteroids; and localized therapies such as radiotherapy, LITT and craniotomy.

The date and nature of the diagnosis (presence or absence of metastasis) of the reference, other equivocal and additional PET (if applicable) lesions reached by site will be collected. An assessment of neurological deterioration will be recorded. The subject mortality status will also be recorded, with collection of date and cause of death (if applicable).

Determination of a subject's mortality status must be verifiable from the medical record, including confirmation of death where applicable or, where alive, a documented clinical interaction (e.g. imaging scan, blood test, consult) taking place on or beyond Day 169. If the site is unable to verify mortality status from the medical record, additional steps will be undertaken, including a review of vital records or a documented phone call to the patient or the patient's family.

Therefore, this Visit comprises predominantly of investigator review of the subject medical record and will take place in the physical absence of the subject. Subjects whose reference or other equivocal lesion(s) continue to be considered at the site level to be equivocal for brain metastasis at Month 6 (Visit 5) will have a final research MRI unless an SoC MRI was performed within the prior 3 weeks.

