7.4.4.6.1 Analysis 1: Subject-Level NPA and PPA on subjects with histopathology or follow-up MRI prior to CNS-directed therapy

Subject-level NPA and PPA (equivalent to specificity and sensitivity, respectively) of ¹⁸F-fluciclovine PET in detecting recurrent brain metastases will be calculated for subjects who either have histopathology available, or have follow-up MRI acquired before new or altered CNS-directed therapy and have lesions with at least 20% increase or 30% decrease in the longest diameter relative to the SoC baseline MRI.

The SoR will be based on CTP determination on the two corresponding domains: histopathology and on MRI findings before new or altered CNS-directed therapy.

- SoR will be positive if one domain is positive and the other domain is positive or non-contributory.
- SoR will be negative if one domain is negative and the other domain is negative or non-contributory.
- SoR will be indeterminate if both domains are non-contributory, or if one domain is positive and the other domain is negative.

7.4.4.6.2 Analysis 2: Subject-Level NPA and PPA on subjects without contributory MRI findings after new or altered CNS-directed therapy

Subject-level NPA and PPA (equivalent to specificity and sensitivity, respectively) of ¹⁸F-fluciclovine PET in detecting recurrent brain metastases will be calculated for subjects who:

[figure not shown]
- have no CNS-directed therapy during follow-up, or
- have non-contributory findings in MRIs acquired after new or altered CNS-directed therapy.

The SoR will be based on the final CTP determination in these subjects.

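### SAP 7.4.5.1 Rule 2 codes an undecided reference lesion as negative when the subject stays neurologically well, without asking whether the lesion was treated after the PET

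*SAP*

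**What the plan says.** SAP 7.4.5.1 handles a reference lesion that the CTP has not called positive or negative: "If the SoR determined by the CTP is not positive/negative then the SoR will be determined using the following rules".

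- Rule 1: "If the subject has neurological deterioration at any time during the 6-months follow-up, the SoR will be assigned to positive".
- Rule 2: the condition is "If the subject is confirmed not to have neurological deterioration on or after day 141" and the result is "even if the subject dies after day 141, the SoR will be assigned to negative".
- Rule 3: "Otherwise the SoR will remain as indeterminate". The main analysis then imputes, for each reader, the opposite of that reader's call.

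None of the three rules mentions treatment of the lesion. The chart that the section refers to is missing from the text available for review, but the rules are written out in full.

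The protocol leaves further treatment to standard of care (4.1), says the PET result may help direct management (2.1.1), and collects treatments to Month 6, including "localized therapies such as radiotherapy, LITT and craniotomy" (10.6). The deterioration assessment in protocol 9.1.8 has a treatment check, "Was not altered by therapies for radiation necrosis". It qualifies only a deterioration that was observed. Where there is none, the site records just the date of the latest supporting clinical record.

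SAP 7.4.4.6 has two sensitivity analyses built around CNS-directed therapy during follow-up. The second keeps untreated subjects and also those who "have non-contributory findings in MRIs acquired after new or altered CNS-directed therapy".

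**The concern.** Rule 2 reads six months without neurological decline as absence of recurrent metastasis. That inference needs the lesion to have run its own course. If it was re-irradiated, ablated, resected without decisive tissue, or exposed to new systemic therapy, the subject may be well because a real recurrence was controlled. Rule 2 then records no recurrence, and that label enters the primary NPA and PPA.

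No planned sensitivity analysis tests these labels. Analyses 1 and 2 in SAP 7.4.4.6 work from CTP determinations on subsets. The reader-majority analysis in 7.4.5.1 varies only subjects still indeterminate after Rules 1 and 2. The central neuroradiologist analysis concerns baseline equivocal status.

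At stake is whether a PET-negative call can be counted as correct when nothing is known about the lesion. Success requires the same two of three readers to meet both goals, so a shift in one reader of the pair could matter.

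**Working it through.** **1. The plan's own threshold (SAP 7.6).** Inputs: 130 evaluable subjects, prevalence 0.5 (so 65 positive and 65 negative), goal 50%, assumed value 70%, one-sided 0.025.

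- P(X ≥ 41 | 65, 0.5) = 0.0232 and P(X ≥ 40 | 65, 0.5) = 0.0408, so 41/65 is the smallest passing count. Its Clopper-Pearson lower limit is 50.2%.
- P(X ≥ 41 | 65, 0.7) = 0.910, which reproduces the stated 90% for each endpoint. For both endpoints, if independent, 0.910² = 0.83. That is used below only as a baseline.

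**2. What each rule does to one treated, CTP-undecided, non-deteriorated subject.**

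| Read | Rule 2 | Rule 3, main analysis | Correct cell if recurrence | Correct cell if none |
|---|---|---|---|---|
| PET-positive | false positive | false positive | true positive | false positive |
| PET-negative | true negative | false negative | false negative | true negative |

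The two rules differ only for PET-negative reads.

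**3. Size against Rule 3.** Suppose a reader scores s/65 on both measures with Rule 2 in force, and k of the true negatives are such subjects. Sending them to Rule 3 gives NPA = (s − k)/(65 − k) and PPA = s/(65 + k). The count k is not in the documents; 1 to 6 of 130 was examined. Lower limits are Clopper-Pearson.

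| s | k | PPA (lower limit) | NPA (lower limit) |
|---|---|---|---|
| 46 | 0 | 46/65 = 70.8% (58.2%) | 46/65 = 70.8% (58.2%) |
| 46 | 4 | 46/69 = 66.7% (54.3%) | 42/61 = 68.9% (55.7%) |
| 46 | 6 | 46/71 = 64.8% (52.5%) | 40/59 = 67.8% (54.4%) |
| 44 | 5 | 44/70 = 62.9% (50.5%) | 39/60 = 65.0% (51.6%) |
| 44 | 6 | 44/71 = 62.0% (49.7%) | 38/59 = 64.4% (50.9%) |
| 43 | 4 | 43/69 = 62.3% (49.8%) | 39/61 = 63.9% (50.6%) |
| 42 | 3 | 42/68 = 61.8% (49.2%) | 39/62 = 62.9% (49.7%) |
| 41 | 1 | 41/66 = 62.1% (49.3%) | 40/64 = 62.5% (49.5%) |

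**4. Size against the truth.** Take a true 46/65 on both measures and let m treated recurrences be coded negative by Rule 2.

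- m = 5, all PET-negative: PPA 46/60 = 76.7%, NPA 51/70 = 72.9%. Both rise.
- m = 5, all PET-positive: PPA 41/60 = 68.3%, NPA 46/70 = 65.7%. Both fall.
- m = 10, all PET-positive: PPA 36/55 = 65.5%; NPA 46/75 = 61.3% with lower limit 49.4%, which misses the goal.

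Now let the m recurrences be read positive at the assumed 70%, one reader, independent tests. At m = 5:

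- Rule 2: expected NPA (65 × 0.7 + 5 × 0.3)/70 = 67.1%, PPA 70.0%, joint power 0.69 against 0.83 at m = 0.
- Rule 3: expected PPA (60 × 0.7)/(60 + 1.5) = 68.3%, NPA (65 × 0.7)/(65 + 3.5) = 66.4%, joint power 0.61.

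At m = 10 the joint power is 0.57 under Rule 2 and 0.39 under Rule 3.

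**The case against.** A reader might infer that Rule 2 biases the primary result in the product's favour. The documents do not support that as a general statement. If these lesions are true recurrences and PET sensitivity is near the assumed 70%, most are PET-positive, and Rule 2 turns those correct calls into false positives. On average that works against the product. The favourable direction holds only relative to Rule 3, and only for PET-negative reads.

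The exposed group is also narrow. A lesion that was resected, or ablated with a planned biopsy, will usually have tissue for central review. The CTP sees histopathology, follow-up MRI and cancer therapies before Rule 2 applies. Whether treated subjects are more often left undecided cannot be settled, because the CTP charter is not among the documents. The table in step 3 takes every moved subject as PET-negative. At 70% sensitivity, 6 PET-negative recurrences imply about 6/0.3 = 20 treated, undecided, non-deteriorated recurrences, a number nothing in the documents supports. Any that were not recurrences were labelled correctly by Rule 2.

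Nor does Rule 3 give a truer label: a PET-positive treated recurrence stays coded negative. The radiation-necrosis check in protocol 9.1.8 should not be read as recognising that treatment can mask recurrence, since it qualifies only an observed deterioration.

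All of this stands and limits the point. It does not remove the gap: Rule 2 treats the absence of decline as evidence in subjects where it is not, and no planned analysis shows how much depends on that.

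**Conclusion.** The point holds in a limited form. Rule 2 has no treatment condition, so in treated, CTP-undecided subjects the primary label is unreliable. The error can go either way against the truth; against the SAP's own worst case it only favours the product. The subjects concerned are mainly those re-treated without tissue or with non-contributory tissue, and their number is unknown.

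Under the assumed 65/65 split, with every moved subject PET-negative, a reader at 46/65 still meets both goals at each count from 1 to 6. A reader at 44/65 misses the PPA goal only at 6. Readers at 43, 42 and 41 miss it at 4, 3 and 1. It would be tempting to conclude that the rule endangers the trial's result; that holds only for readers near the threshold, and the success criterion depends on two readers together. This is an inexpensive improvement that should be made. It does not show that the primary analysis is invalid.

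**What to change.** Restrict Rule 2 to subjects whose reference lesion had no resection, LITT, radiotherapy or other started or changed CNS-directed therapy between the PET and the date on which absence of deterioration is confirmed. Send the others to Rule 3. Define the CNS-directed therapy term in the SAP, because 7.4.4.6 uses it without a definition and the reach of the clause depends on it, for example for therapy given for radiation necrosis.

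At minimum, keep Rule 2 and pre-specify a sensitivity analysis of the primary endpoint that sends those treated subjects to Rule 3. In either case, report how many subjects Rule 2 classifies, by treatment status and by PET result for each reader.

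The cost is one clause and one definition, or one extra analysis. Therapy data are already collected to Month 6, and patient care does not change. PPA and NPA become less favourable, and the power loss in step 4 could be material if many subjects were affected. Rule 3 should be presented as a conservative bound, since for PET-positive reads it gives the same label as Rule 2.

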15.1. Estimation of Sample Size

Approximately 150 subjects will be enrolled, to obtain 130 evaluable subjects.

A one-sample binomial exact test will be used to test the following hypotheses in NPA and PPA of ¹⁸F-fluciclovine PET:

NPA

- $H_0(\text{NPA})$: NPA of PET $\leq \text{NPA}_0$
- $H_1(\text{NPA})$: NPA of PET $> \text{NPA}_0$

PPA

- $H_0(\text{PPA})$: PPA of PET $\leq \text{PPA}_0$
- $H_1(\text{PPA})$: PPA of PET $> \text{PPA}_0$

Where NPA_0 and PPA_0 are performance goals for NPA and PPA, respectively.

Performance goals of 50% (NPA_0) for NPA and 50% (PPA_0) for PPA were selected as acceptable thresholds given the setting where SoC imaging is already equivocal. The lower limits for the exact 95% confidence intervals (CI) (Clopper-Pearson method) for both NPA and PPA should be greater than 50%. Assuming an NPA of at least 70% and a PPA of at least 70% for ¹⁸F-fluciclovine PET would need to be observed, a sample size of 130 would achieve 90% power at a 1-sided significance level of 0.025 to reject the performance goals for both NPA and PPA; assuming a brain metastasis prevalence rate of 0.5.

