7.2 Analysis Sets

The Full Analysis Set (FAS) will include all enrolled subjects dosed with IMP with an evaluable Visit 2 on-study PET scan. The FAS will be used for primary and secondary non-safety endpoints (including diagnostic performance and inter-reader and intra-reader assessment for the PET scans).

The Safety Analysis Set (SAF) will include all subjects dosed with IMP (with or without the associated PET scan). The SAF will be used for all safety analyses.

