7.4.4.2 Lesion-Level Diagnostic Performance

Lesion-level diagnostic performance (lesion-level PPA, NPA, PPV and NPV) will be calculated based on BIE of ^{18}F -fluciclovine PET compared to SoR on all lesions (reference, other equivocal and additional PET lesions) as determined by CTP (i.e. if CTP decides that the lesion SoR is indeterminate, then the lesion will not be counted in this lesion-level diagnostic performance). Point estimates and 95% 2-sided confidence intervals will be presented.

The confidence interval will be calculated based on the methodology described by Zhou et al, for lesion-level PPA, NPA, PPV and NPV. The formula for PPV is:

$$\widehat{PPV} = \sum_p TP_p / \sum_p Pos_p$$
$$\widehat{Var}(\widehat{PPV}) = \frac{1}{P(P-1)} \sum_p \left(\frac{Pos_p}{\overline{Pos}} \right)^2 (\widehat{PPV}_p - \widehat{PPV})^2$$

With:

P	: (number of) Patients
p	: individual patient
Pos_p	: Number of positive regions for patient p
TP_p	: Number of true positive regions for patient p
$\overline{Pos} = \sum_p Pos_p / P$: Mean cluster size
$\widehat{PPV}_p = TP_p / Pos_p$: Patient PPV

The example in Zhou et al. is coded in SAS in Appendix 1.

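### Reference lesions with no resolved standard of reference count as PET errors for every reader; no subject-level table on resolved subjects is planned, and the stated 90% power makes no allowance for this.

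*SAP*

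**What the plan says.** SAP 7.2 sets the population for the primary endpoint: "The Full Analysis Set (FAS) will include all enrolled subjects dosed with IMP with an evaluable Visit 2 on-study PET scan". A known SoR is not a condition of entry.

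Under SAP 7.4.5.1, if the Central Truth Panel (CTP) does not call the reference lesion positive or negative, two rules apply. Neurological deterioration at any time in the six months makes the SoR positive (rule 1). Confirmed absence of deterioration on or after day 141 makes it negative (rule 2). Anything else stays indeterminate, and the SAP continues: "All subject-level analysis involving SoR will be presented twice, by imputing the remaining indeterminate results as follows".

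- Main analysis: "for each PET reader, the worst case according to that reader (i.e. the opposite finding to the individual PET reader finding) will be imputed".
- Second presentation: "the worst case according to the majority of PET readers (i.e. the opposite finding to the PET finding of at least 2/3 PET readers").

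The other relevant analyses are:

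- SAP 7.4.4.6.1 is limited to subjects with histopathology, or with a size change on MRI before new or altered CNS-directed therapy.
- SAP 7.4.4.6.2 is limited to subjects without contributory MRI after such therapy. There, "The SoR will be based on the final CTP determination in these subjects".
- A conditional analysis in SAP 7.4.5.1 is run "using only subjects with central neuroradiologist confirmation of the reference equivocal lesions".
- At lesion level (SAP 7.4.4.2), "if CTP decides that the lesion SoR is indeterminate, then the lesion will not be counted in this lesion-level diagnostic performance".

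On power, Protocol 15.1 states: "a sample size of 130 would achieve 90% power at a 1-sided significance level of 0.025 to reject the performance goals for both". The pair meant is the two primary endpoints, at rates of 70% against goals of 50% and a prevalence of 0.5. SAP 7.6 repeats this. Neither mentions unresolved SoR.

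**The concern.** Setting the SoR opposite to a reader's own call makes the subject an error for that reader by construction. In the main analysis this happens to all three readers, so on a split read one subject carries different truths for different readers. The second presentation also imputes. It relieves only a dissenting reader, who is then scored correct, so it does not show what the rule costs.

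None of the other analyses fills the gap. The two in SAP 7.4.4.6 and the neuroradiologist-confirmed one select subjects on other grounds. The lesion-level analysis does drop indeterminates, but it pools reference, other equivocal and additional PET lesions.

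Two things are at stake. If the main result falls just short of the pass mark, the planned subject-level tables cannot show whether PET misread lesions or the truth was never established; PPV and NPV carry the same forced errors. And a reader of the sample-size section is given a power figure that leaves this mechanism out.

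**Working it through.** **Inputs.** From Protocol 15.1 and SAP 7.6: goals of 50%, true rates of 70%, one-sided 0.025, prevalence 0.5, and 130 subjects, hence 65 SoR-positive and 65 SoR-negative. From SAP 7.4.3: a goal is met when the Clopper-Pearson lower 95% limit exceeds 50%. The number unresolved, M, appears nowhere and is an assumption.

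**Reproducing the stated figure.** Let c(n) be the smallest count out of n whose lower limit exceeds 50%. c(65) = 41, that is 63.1%, with exact one-sided alpha 0.023. Per-endpoint power is P[Bin(65, 0.7) ≥ 41] = 0.910. PPA and NPA use different subjects, so power for both is 0.910 × 0.910 = 0.83. The stated 90% is therefore a one-reader, one-endpoint figure with every SoR resolved.

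**Adding unresolved subjects.** With 70% / 70% and prevalence 0.5, the chance of a positive read is 0.5 × 0.7 + 0.5 × 0.3 = 0.5. So M/2 forced errors are placed in each denominator. There are two cases:

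- Case A: 130 resolved plus M unresolved. Power = P[Bin(65, p) ≥ c(65 + M/2)]. This fits scanned early withdrawals, who may be replaced (Protocol 13.2) but still meet the Full Analysis Set definition.
- Case B: M unresolved inside the 130. Power = P[Bin(65 − M/2, p) ≥ 41]. This fits unresolved subjects who are not replaced, such as some deaths, which Protocol 10.7 does not count as early withdrawal.

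The comparator for B is the same data analysed on resolved subjects only: P[Bin(65 − M/2, p) ≥ c(65 − M/2)]. For A it stays at 0.91. The critical values are c(67) = 42, c(70) = 44 and c(73) = 46 for A, and c(63) = 40, c(60) = 39 and c(57) = 37 for the comparator.

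Per-endpoint, one-reader power at p = 0.70:

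| M | A | B | B data, resolved only | B: due to the rule |
|---|---|---|---|---|
| 0 | 0.91 | 0.91 | 0.91 | 0 |
| 4 | 0.86 | 0.84 | 0.90 | 0.06 |
| 10 | 0.71 | 0.67 | 0.84 | 0.17 |
| 16 | 0.51 | 0.44 | 0.84 | 0.40 |

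At M=2, B and its comparator are both 0.88, so in that case the rule costs nothing.

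**Check on the even split.** If the split of unresolved reads is Binomial(M, 0.5), A becomes 0.84, 0.69 and 0.53 at M = 4, 10 and 16.

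**Where the expected result drops below the pass mark (even M).** In A, at M=16: 45.5/73 = 62.3% against 46/73 = 63.0%. In B, at M=14: 0.7 × 58/65 = 62.5% against 63.1%.

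**Higher accuracy, M=10 (A / B).** True 75%: 0.93 / 0.91. True 80%: 0.99 / 0.99. At the low ends that Protocol section 2 quotes for other amino acid tracers (sensitivity 79%, specificity 84%), power for both endpoints is 0.99 / 0.98.

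The requirement that the same two of three readers meet both goals is not modelled, so none of these is study-level power.

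**The case against.** The strongest reply is that M could be very small. To stay unresolved, a subject needs no verdict from a five-specialty panel with up to six months of data (Protocol 11.8.2), no qualifying deterioration, and no confirmed absence of deterioration on or after day 141, which suffices even if the subject dies later. Surviving subjects with a still-equivocal reference lesion get a Month 6 MRI unless a recent one exists (Protocol 9.1.5.2). This stands: the documents give no value for M, and the loss matters only if M is not small and true accuracy is near 70%.

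Second, a reader might charge all of the Case B loss to the rule. That is not supported. At M=10 power falls from 0.91 to 0.67, but a resolved-only analysis of the same data reaches 0.84, so 0.07 is lost sample size and discreteness and 0.17 is the rule.

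Third, the sample-size text speaks of 70% as a rate to be observed, which could mean the rate after imputation. The wording permits this, but the text does not say it, and the plan contains no higher pre-imputation rate that would go with it.

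Fourth, a resolved-only table favours PET and may be selective, because early death or withdrawal is a route to being unresolved. It would also keep SoR values assigned by rules 1 and 2, which are themselves imputations. This is a good reason to keep it as a sensitivity analysis, not a reason to omit it.

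Fifth, the SAP introduction refers to table and listing templates that are not in the text reviewed, so the table could exist there. The claim is limited to the visible text. Listings (SAP 7.1.1) and the SoR prevalence summary (SAP 7.3.3) would allow such a table, but only post hoc.

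**Conclusion.** The point holds as a matter of interpretation and of the power statement, not of validity. Every residual indeterminate is an error for every reader in the main analysis, and no visible subject-level analysis covers all Full Analysis Set subjects with a resolved SoR.

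Three stronger readings should be resisted:

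- That the rule could produce a false success. It cannot: it only adds errors.
- That the stated 90% is right as long as no SoR is unresolved. It is then right per endpoint (0.91), but not for both endpoints as the text claims (0.83).
- That the trial is shown to be underpowered. The documents do not give M. At the 70% planning rate the loss is about 5 to 7 points at M=4 and 20 to 24 points at M=10, counted from 0.91 and including sample loss in Case B. At 80% and M=10 it is negligible.

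These sizes rest on prevalence 0.5, an even split of unresolved reads, and one reader.

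**What to change.** 1. In SAP 7.4.5.1, keep the worst-case main analysis. Add a prespecified sensitivity analysis of subject-level PPA, NPA, PPV and NPV in Full Analysis Set subjects whose SoR is positive or negative by the CTP or by rules 1 and 2. Report the number unresolved, with reasons, and note beside the table that it is more favourable to PET and may be selective.

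2. In Protocol 15.1 and SAP 7.6, restate the power: about 91% per endpoint for one reader with every SoR resolved; about 83% for both endpoints under the same conditions; lower with unresolved SoR, with values for a range of M (for example 0, 4, 10 and 16). Say whether the 70% is meant before or after imputation.

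Enrolment does not change. The cost is one more table set, a few lines of text, and a less favourable stated power. The change discloses the loss; it does not remove it.
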